13. MEDICAL HISTORY

The following variables will be summarized:

- Any past or concomitant diseases? (Y/N)
- Any past surgeries for reasons other than Ulcerative Colitis? (Y/N)

Additionally, medical history and concomitant medical conditions will be coded using the Medical Dictionary for Regulatory Activities (MedDRA) and summarized by System Organ Class (SOC) and Preferred Term (PT) within each of these categories (historical vs concurrent). A concomitant condition is one having ongoing status = Yes, as collected in the Medical History eCRF. Adverse events occurring prior to randomization and on or after signing ICF will be captured as Medical History.

For the Induction Period Analysis, these summaries will be presented by planned treatment group and overall for the FAS, mFAS, and PP Set.

Listings will be provided for all medical history findings.

14. PRIOR AND CONCOMITANT MEDICATIONS

Medications will be coded using the WHO Drug Dictionary, utilizing Anatomical Therapeutic Chemical (ATC) Therapeutic Main Group (Level 2) and Chemical Subgroup (Level 4). Listings will be provided and will additionally include ATC Level 5, separately, for all prior and concomitant medications.

14.1 UC MEDICATIONS

Medications taken for UC will be considered prior UC medications if the start date of the medication is prior to the Informed Consent date. Otherwise, they are considered concomitant UC medications.

For the Induction Period Analysis, summaries of prior and concomitant UC medications will be separately presented by planned treatment group and overall for the Safety, FAS, mFAS, and PP sets. At study end, summaries will be presented by planned treatment group for FAS-ET population. Medications flagged as ‘rescue medications’ (see [Section 25](#), Appendix IV) will be considered concomitant UC medications and will be flagged in listings.

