6.10.1 Allowed Medications for the Treatment of Ulcerative Colitis

Oral 5-ASA, oral corticosteroids, or medicinal probiotics are allowed at the time of Screening; however, these products should not be started during Screening or during the treatment period in participants who are not already receiving them.

Immunosuppressive agents such as oral AZA or 6-MP must be discontinued > 2 weeks prior to Screening endoscopy.

Participants receiving 5-ASA or medicinal probiotics should maintain a stable dose throughout the Screening Period and study and can only be discontinued or reduced in dose if Investigator judgment requires it because of toxicity or medical necessity.

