6.10.1.1 Corticosteroid Therapy

Oral corticosteroid therapy (prednisone at a stable dose of ≤ 20 mg/day, budesonide at a stable dose of ≤ 9 mg/day, or equivalent steroid) is allowed to be continued during the 13-week Induction Treatment Period provided the dose has been stable for the 2 weeks immediately prior to the Screening endoscopy assessment.

Participants entering the LTE Treatment Period will be tapered from corticosteroids. Participants entering the OLE Treatment Period may be tapered after 13 weeks of treatment in the OLE. The recommended tapering schedule for oral corticosteroids (other than budesonide extended release tablets [budesonide MMX]) is as follows:

- Dose > 10 mg/day prednisone or equivalent: taper daily dose by 5 mg/week until receiving 10 mg/day, and then continue tapering by 2.5 mg/week until 0 mg/day
- Dose ≤ 10 mg/day prednisone or equivalent: taper daily dose by 2.5 mg/week until 0 mg/day

The recommended tapering schedule for participants receiving oral budesonide MMX 9 mg/day is to reduce tablets to 9 mg two days out of three for 2 weeks, followed by 9 mg one day out of three for 2 weeks, and then discontinue.

For participants who cannot tolerate the corticosteroid taper without recurrence of clinical symptoms of either UC or steroid withdrawal, the corticosteroid dose may be increased (up to the dose at study entry if required), but tapering should be attempted again within 2 weeks.

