14.2 OTHER MEDICATIONS

Medications not taken for Ulcerative Colitis will be considered prior medications if the end date of the medication is prior to the date of first dose of study treatment. Otherwise, they are considered concomitant medications.

A medication is considered concomitant for the Induction Treatment Period if it meets the following conditions:

- a) Medication started or was ongoing on or after the first study treatment administration date
and
- b) Medication started or was ongoing on or before Visit 7
or
Medication started or was ongoing on or before any of the Early Termination/1-Week Follow-up/2-Week Follow-up visits for participants that permanently discontinue study treatment during the Induction Treatment Period (and are therefore discontinued from the study).

A medication is considered concomitant for the entire study if meets the following conditions:

- c) Medication started or was ongoing on or after the first study treatment administration date
and
- d) Medication study treatment was ongoing on or before the two-week follow-up visit.

Imputation rules specified in Section 10.1 will be applied to partial/missing dates.

Three summaries will be created:

- Prior medications will be summarized by planned treatment group and overall for the FAS, mFAS, and PP sets.
- Concomitant medications taken during the Induction Treatment Period will be summarized by planned treatment group and overall for the Safety, FAS mFAS, and PP sets. This summary will be generated for the Induction Period Analysis.

- Concomitant medications taken during the entire study summaries will be summarized by planned treatment group and overall for FAS ET and PP populations. This summary will be generated at study end.

Additionally, the use of P-gp or BCRP transporters during the study will be flagged in participant-level dataset(s) and in listings. Please see [Section 25](#) (Appendix IV) for WHO Drug Dictionary (WHODD) ATC codes specifying P-gp and BCRP transporters.

If prior medications for UC are inadvertently entered on eCRF pages intended for concomitant medications, these records will be treated as prior medications.

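### SAP 14.1 sorts UC drugs by start date alone, so nearly all permitted background UC therapy taken during Induction is tabulated as prior and mixed with historical treatment

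*SAP*

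**What the plan says.** SAP 14.1 gives the rule for UC drugs in two sentences. The first is "Medications taken for UC will be considered prior UC medications if the start date of the medication is prior to the Informed Consent date". The second is "Otherwise, they are considered concomitant UC medications". There is no end-date test, no test of ongoing use and no category for a drug that is both. Drugs flagged as rescue under Appendix IV "will be considered concomitant UC medications and will be flagged in listings". Prior and concomitant UC medications are then summarized separately, by planned treatment group and overall.

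SAP 14.2 uses a different rule for all other drugs. It begins "Medications not taken for Ulcerative Colitis will be considered prior medications if the end date of the medication is prior" and takes first dose as the cut-off. It defines concomitant for Induction as started or ongoing on or after first dose and on or before Visit 7, or the early termination or follow-up visits for those who stop. The section closes with a sentence on UC drugs: "If prior medications for UC are inadvertently entered on eCRF pages intended for concomitant medications, these records will be treated as prior medications".

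The protocol permits three kinds of background UC therapy: oral 5-ASA, oral corticosteroids and probiotics. On when they may begin, Protocol 6.10.1 says "these products should not be started during Screening or during the treatment period in participants who are not already receiving them". On continuation it says "Participants receiving 5-ASA or medicinal probiotics should maintain a stable dose throughout the Screening Period and study". Protocol 6.10.1.1 says that a stable oral corticosteroid dose "is allowed to be continued during the 13-week Induction Treatment Period". Protocol 6.10.2 prohibits other UC treatments for the whole study.

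**The concern.** A table of concomitant UC medications should tell the reader what UC treatment each arm was taking while the Week 13 outcome was being formed. Background 5-ASA and corticosteroids are the permitted drugs most able to influence that outcome. Under SAP 14.1 they are nearly all placed in the other table, where a course taken daily to Week 13 cannot be told apart from one that ended years before. A reader who takes the table title at face value could conclude that few participants were on background therapy.

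The label also departs from the protocol's own usage. Inclusion criterion 10 lists these same products as permitted concomitant medications. For 5-ASA and oral corticosteroids it distinguishes participants on a stable dose from those who stopped at least 2 weeks before the Screening endoscopy. SAP 14.1 puts both groups in one table. SAP 18, which lists departures from the protocol's analysis, does not mention this.

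**Working it through.** The plan states no figure on this point, so the check is to read the rules together and run them on example records.

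1. **When permitted background therapy starts.** Protocol 6.10.1 rules out starting it during Screening or treatment. The Schedule of Activities places informed consent in Screening. A permitted background drug therefore starts before consent.
2. **Whether it continues after first dose.** Yes: 5-ASA and probiotics at a stable dose (Protocol 6.10.1), and oral corticosteroids through Induction (Protocol 6.10.1.1).
3. **How SAP 14.1 classes it.** Start before consent means prior, whatever happens later.
4. **What is left as concomitant.** Drugs first started on or after consent, plus flagged rescue drugs. Given Protocol 6.10.1 and 6.10.2, these are mainly rescue or non-permitted.

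The example records below assume consent on 2 May 2022 and first dose on 30 May 2022. Partial start dates are imputed as in SAP 10.1: a year-only start before the year of first dose becomes 15 July of that year, a year-only start in the year of first dose becomes the first-dose date, and a wholly missing date is not imputed. The last column applies the SAP 14.2 test (prior only if ended before first dose).

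| Example record | SAP 14.1 | SAP 14.2 test |
|---|---|---|
| 5-ASA from 1 March 2019, ongoing | prior | concomitant |
| Prednisone from 10 April 2022, ongoing, stable | prior | concomitant |
| 5-ASA, January 2018 to January 2020 | prior | prior |
| New rescue prednisone, 8 July 2022 | concomitant | concomitant |
| 5-ASA, start year 2021 only, ongoing | prior | concomitant |
| 5-ASA, start year 2022 only, ongoing | concomitant | concomitant |
| 5-ASA, start date wholly missing, ongoing | concomitant | concomitant |
| Permitted 5-ASA reduction logged as a new line, 20 June 2022 | concomitant | concomitant |
| Steroid restarted after an LTE taper, within entry dose, 20 October 2022 | concomitant | concomitant |

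The first three rows carry the point: under SAP 14.1, two drugs in use throughout Induction share a category with one stopped in 2020, and the SAP 14.2 test separates them. The last four rows are the exceptions, in which a permitted drug reaches the concomitant table. Two arise from incomplete dates. One depends on a logging convention that the documents do not give. The last concerns the LTE, so it touches only the study-end table.

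**What else shows background use.** For corticosteroids, SAP 12 tabulates stable use as collected in both IWRS and EDC. For 5-ASA, SAP 12 has only prior failure of oral 5-ASA alone, and the SAP 10.5 subgroups use prior oral 5-ASA-only treatment or failure. None of these 5-ASA items shows who was taking it during Induction.

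**The case against.** The strongest reply is that little is lost. Background 5-ASA does appear by arm, in the prior-UC table for the Safety, FAS, mFAS and Per Protocol sets, and every record is listed. Baseline corticosteroid use is a randomization factor, a stratification factor in the primary Cochran-Mantel-Haenszel test, a subgroup and a baseline characteristic. Because the dose should be stable through Induction, that flag is a fair proxy for steroid use on treatment. SAP 14.1 states its definition openly, and the table shells are in a separate file that may carry an ongoing flag.

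Much of this stands. It rules out two stronger readings that a reader might infer:

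- **That 5-ASA use appears in no summary, or that steroid balance is hidden.** The prior table by arm and SAP 12 contradict both. What is missing is the split between ongoing and past 5-ASA use.
- **That no permitted background record can reach the concomitant table.** The exceptions in the working show that a few can.

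The reply does not repair the rule. The SAP text calls for no ongoing flag for UC drugs, and listings leave the by-arm count to be rebuilt by hand. Nor can SAP 14.2 be read as already covering UC drugs: its opening test is limited to drugs not taken for UC, and its closing sentence sends prior UC records back to the prior category.

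**Conclusion.** The point holds as a defect in the descriptive medication tables. Nearly all permitted background UC therapy taken during Induction will be labelled prior and merged with historical therapy, and the concomitant-UC table will consist mainly of rescue or non-permitted drugs. The practical gap is concurrent 5-ASA use by arm, and probiotics where they are recorded as taken for UC.

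A reader might infer that the efficacy results are affected; the documents do not support that. The primary test uses as-randomized strata. Rescue status follows the exposure and change-from-baseline rules of Appendix IV under blinded review. Per Protocol membership rests on compliance and deviations (SAP 8). None of these uses the prior or concomitant label.

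The number of participants affected cannot be given: the documents report no prevalence of background 5-ASA, steroid or probiotic use, and the planned 189 is only a ceiling. The conclusion assumes that Protocol 6.10.1 is followed, that start dates are mostly complete, and that the unseen table shells add no ongoing-use split. The change should be made, but the primary analysis does not depend on it.

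**What to change.** In SAP 14.1, apply the on-treatment rule of SAP 14.2 to UC drugs:

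- Concomitant for Induction if started or ongoing on or after first dose and on or before Visit 7, or the early termination or follow-up visits for those who stop, whatever the start date.
- Prior only if ended before first dose.
- Flagged as both if started before first dose and continued after it.

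Limit the last sentence of SAP 14.2 to drugs that ended before first dose. Show rescue drugs as a sub-block of the concomitant-UC table, so that background and rescue use can be read apart.

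The cost is SAP wording and one derivation in the medication dataset. Protocol 6.10 already collects concomitant medications from Screening to the 2-Week Follow-Up visit, so no new data or protocol amendment should be needed, provided the UC medication page records end date or ongoing status, as SAP 14.2 presumes for other drugs.

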14.2 OTHER MEDICATIONS

Medications not taken for Ulcerative Colitis will be considered prior medications if the end date of the medication is prior to the date of first dose of study treatment. Otherwise, they are considered concomitant medications.

A medication is considered concomitant for the Induction Treatment Period if it meets the following conditions:

- a) Medication started or was ongoing on or after the first study treatment administration date
and
- b) Medication started or was ongoing on or before Visit 7
or
Medication started or was ongoing on or before any of the Early Termination/1-Week Follow-up/2-Week Follow-up visits for participants that permanently discontinue study treatment during the Induction Treatment Period (and are therefore discontinued from the study).

A medication is considered concomitant for the entire study if meets the following conditions:

- c) Medication started or was ongoing on or after the first study treatment administration date
and
- d) Medication study treatment was ongoing on or before the two-week follow-up visit.

Imputation rules specified in Section 10.1 will be applied to partial/missing dates.

Three summaries will be created:

- Prior medications will be summarized by planned treatment group and overall for the FAS, mFAS, and PP sets.
- Concomitant medications taken during the Induction Treatment Period will be summarized by planned treatment group and overall for the Safety, FAS mFAS, and PP sets. This summary will be generated for the Induction Period Analysis.

- Concomitant medications taken during the entire study summaries will be summarized by planned treatment group and overall for FAS ET and PP populations. This summary will be generated at study end.

Additionally, the use of P-gp or BCRP transporters during the study will be flagged in participant-level dataset(s) and in listings. Please see [Section 25](#) (Appendix IV) for WHO Drug Dictionary (WHODD) ATC codes specifying P-gp and BCRP transporters.

If prior medications for UC are inadvertently entered on eCRF pages intended for concomitant medications, these records will be treated as prior medications.

15. EXPOSURE AND TREATMENT COMPLIANCE

The Safety Set will be used for all exposure and compliance tabulations and listings.

Titration blister packs contain a varying and nondecreasing number of tablets for each study day of titration. Maintenance blister packs contain a fixed number of tablets for each study day of maintenance. Bottles contain a fixed number of tablets intended to provide the study participant with three tablets per day between site visits, plus overage to account for visit scheduling.

Blister packs are dispensed to study participants for the Induction Treatment Period and LTE – no bottles are dispensed. During OLE, participants are dispensed blister packs for titration purposes only; after titration, participants are dispensed study treatment in bottles.

Participant eDiary data will not be used for any purpose related to exposure or treatment compliance. Exposure and compliance tables and listings will rely exclusively on data as collected in EDC and IWRS.

15.1 Treatment Exposure

Treatment exposure (duration in days, number of tables expected, number of tablets taken, number of tablets missed, compliance, dose interruptions, and overdoses) will be summarized descriptively. For the interim database lock and unblinding associated with the Induction Treatment Period, treatment exposure will be tabulated for the Induction Treatment Period only. Participant listings will be generated.

15.1.1 Duration

Per-participant Treatment Duration will be calculated as (Participant Date of Last Study treatment – Participant Date of First Study treatment) + 1, using appropriate first and last dates, and expressed in days. Interruptions, compliance, and dose changes are not taken into account for duration of exposure.

For specific study periods (such as Induction, LTE, or OLE), the per-participant first and last dates will be the first and last treatment dates within the given study period. The per-participant

first and last treatment dates will be the least recent and most recent treatment dates across all applicable study periods for that participant.

- Induction
 - Date of first study treatment will be taken from the Study treatment Administration on Site form for the Visit 2 Week 0 site visit.
 - Date of final study treatment will be taken from the End of Induction Treatment Period form.
- LTE
 - Date of first study treatment will be taken from the “Start Date of Administration” field from the “Study Drug Compliance – LTE” form.
 - Date of final study treatment will be taken from the End of Long Term Extension Period form.
- OLE
 - Date of first study treatment will be taken from the “Start Date of Administration” field from the “Study Drug Compliance – OLE” form.
 - Date of final study treatment will be taken from the End of Open Label Extension Period form

15.1.2 Tablets Taken, Missed Doses, and Dose Interruptions

The Study treatment Titration (and Study treatment Re-Titration for participants needing it), Study treatment Compliance, Study treatment Overdose, and Study treatment Administration on Site forms will be used to capture drug exposure. Based on these data for the Induction Treatment Period, the following will be calculated:

- Number of tablets taken = total dispensed – total returned
- Number of tablets expected to be taken = number of tablets a participant should have taken between their first and last study treatment administration
- Number of incomplete doses = number of instances where the number of tablets taken in a study day is less than the number tablets the participant should have taken for that study day
- Number of missed doses = number of instances where the participant takes no tablets for a given study day

These will be summarized for the Induction Treatment Period and will also be listed.

The frequency and percentage of participants who had at least 1 dose interruption, who had at least 1 dose interruption of > 7 days, who had at least 1 dose interruption of > 14 days, who had 1

overdose, and who had > 1 overdose will be summarized for the Induction Treatment Period. Interruption is defined as at least one day of missed dose.

